Progestin Primed Double Stimulation Protocol Versus Flexible GnRH Antagonist Protocol in Poor Responders

ClinicalTrials.gov ID: NCT04537078
Date:01/26/2022

AIM OF THE WORK

The primary aim of this work is to assess the difference between the progestin primed double stimulation protocol and the conventional GnRH antagonist protocol in poor responders regarding the number of M2 oocytes retrieved, the fertilization rate, the resultant embryos number, the implantation rate and the clinical pregnancy rate.

While the secondary aims are:

1. Assessing the difference in the ongoing pregnancy rate in both protocols.
2. Assessing the difference between the follicular phase and the luteal phase of the progestin primed double stimulation protocol regarding the total days of controlled ovarian hyperstimulation, the total gonadotropin dosage, the number of M2 oocytes retrieved ,the fertilization rate and the resultant embryos number.
3. Assessing the difference between the follicular phase of the progestin primed double stimulation protocol and the first round of the conventional GnRH antagonist protocol regarding the number of M2 oocytes retrieved the fertilization rate and the resultant embryos number.

PATIENTS

This study is a randomized controlled study performed at infertility and assisted reproduction unit of El-Shatby Maternity Hospital and Madinah Fertility center.

Sample size:

Sample size calculation is done by the staff members of Medical Research Institute, Alexandria University using NCSS PASS statistical software version 20.

Participants:

The study will be conducted on 80 infertile women indicated for ICSI with criteria of poor ovarian response defined by Bologna criteria (15)

All participants will be informed about the nature of the study and informed consent will be taken from all of them.

Inclusion criteria:

1. Indicated infertile women for ICSI of poor responders defined by Bologna criteria either two or more of the following:(15)

- (i) advanced maternal age or any other risk factor for POR.
- (ii) a previous POR ; less than 3-5 oocytes retrieved per cycle.
- (iii) an abnormal ovarian reserve test (ORT): AFC less than 5-7 or AMH is less than 1.1 ng/ml.

Or two episodes of POR after maximal stimulation are sufficient to define a patient as poor responder in the absence of advanced maternal age or abnormal ORT.

Exclusion criteria:

- 1. Male factor infertility due to azoospermia.
- 2. Patients with uncorrected uterine pathology.

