The fertilization check, which will be performed 16 to 20 hours after ICSI. The resultant embryos will be scored, and they will be vitrified for subsequent transfer.

IV. Embryo transfer

- Starting from the next menstrual cycle Day 3, patients will receive oral estradiol valerate (Cyclo-Progynova (white tablets); Bayer, Germany) daily. From Day 10 onwards, endometrium growth will be monitored by transvaginal ultrasound. When endometrial thickness \geq 7 mm. Progesterone administration (as 800 mg/day vaginal suppositories per day and 100 mg ampule IM every other day) will be initiated and Embryo transfer will be scheduled on Day 3, 4 or 5 with maximum number of 3 class A embryos whether of cleavage or blastocyst stage.

V. Luteal support

- Progesterone administration (as 800 mg/day vaginal suppositories per day and 100 mg ampule IM every other day) will be continued until pregnancy testing 18 days after embryo transfer. The pregnant cases will continue the luteal support till the 12 weeks of gestation.

Group 2:**VI. The flexible GnRH antagonist protocol controlled ovarian stimulation**

This controlled ovarian stimulation will be done twice in two different cycles

In each cycle:

a) luteal phase priming using combined contraceptive pills from day 21 of the previous cycle for one week (0.03 mg ethinyl estradiol, gestodene 0.075 mg, Gynera tab, Bayer Pharma AG., Berlin, Germany).

b) Controlled ovarian hyper-stimulation using antagonist protocol will be used. Stimulation with 225-375 IU of gonadotropins will be started day 2-3 of menses after vaginal ultrasound confirming the absence of ovarian cysts.

c) GnRH antagonist (Cetrotide , Merck Serono, Darmstadt, Germany) will be given daily as the biggest oocyte reaches size 14 mm.

d) Patient response will be monitored by:

1. Transvaginal follicular scanning and the dose of the gonadotropins will be modified according to the response.

2. Serum estradiol.

3. Serum progesterone on the day of triggering.

e) GnRh agonist triggering (Decapeptyl, Ferring, Saint-Prex Switzerland) in a dose of 2 ampules 0.2 mg will be administered when leading follicle >18 mm in diameter. While in the second cycle HCG triggering (Choriomon, IBSA, Lugano, Switzerland) in a dose of 10,000 IU will be administered when the leading follicle >18 mm in diameter.

f) Oocyte pickup will be done 36 hours after GnRh administration.

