g) After the pick-up, oocytes will be denuded. The denuded oocytes are then assessed for nuclear status. Mature oocytes will be used for ICSI.

VII. Fertilization and embryo quality:

The fertilization check, which will be performed 16 to 20 hours after ICSI. The resultant embryos will be scored.

Embryos of the first cycle will be vitrified while embryos of the second cycle will be freshly transferred unless there is excess for vitrification for subsequent trials of transfer.

VIII. Embryo transfer

- Progesterone administration (as 800 mg/day vaginal suppositories per day and 100 mg ampule IM every other day) will be initiated on the day of the oocyte pick up of the second cycle. Embryo transfer will be scheduled on Day 3, 4 or 5 with maximum number of 3 class A embryos whether of cleavage or blastocyst stage that will be a mixture of the thawed embryos of the first cycle and fresh embryos of the second cycle.

IX. Luteal support

Progesterone administration (as 800 mg/day vaginal suppositories per day and 100 mg ampule IM every other day) will be continued until pregnancy testing 18 days after embryo transfer. The pregnant cases will continue the luteal support till the 12 weeks of gestation.

Statistical analysis

Statistical analysis of the data

Data were fed to the computer and analyzed using IBM SPSS software package version 20.0. (Armonk, NY: IBM Corp) Qualitative data were described using number and percent. The Kolmogorov-Smirnov test was used to verify the normality of distribution Quantitative data were described using range (minimum and maximum), mean, standard deviation, median and interquartile range (IQR). Significance of the obtained results was judged at the 5% level.

The used tests were

1 - Chi-square test

For categorical variables, to compare between different groups

2 - Fisher's Exact or Monte Carlo correction

Correction for chi-square when more than 20% of the cells have expected count less than 5

3 - Student t-test

For normally distributed quantitative variables, to compare between two studied groups

4 - Mann Whitney test

For abnormally distributed quantitative variables, to compare between two studied groups

5 -Wilcoxon signed ranks test

For abnormally distributed quantitative variables, to compare between two periods

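### Optional gain: the planned tests of M2 oocytes and embryo number use no baseline data; ANCOVA on age, AMH and centre breaks even once these explain about 3.5 to 4% of the variance

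*Combined protocol and SAP*

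**What the plan says.** The primary aim compares the two protocols "regarding the number of M2 oocytes retrieved, the fertilization rate, the resultant embryos number, the implantation rate and the clinical pregnancy rate". Two of these outcomes, M2 oocytes and embryo number, are counts per woman.

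The Statistical analysis section lists five procedures: chi-square, Fisher's exact or Monte Carlo, Student t, Mann-Whitney and Wilcoxon signed ranks. For a count compared between groups, the choice is the t-test ("For normally distributed quantitative variables, to compare between two studied groups") or Mann-Whitney ("For abnormally distributed quantitative variables, to compare between two studied groups"). No listed procedure takes a covariate, and neither adjustment nor stratification by centre is mentioned.

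Baseline information is available:

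- **AMH** is among the hormonal investigations under Work up.
- **Centre**: the trial is "performed at infertility and assisted reproduction unit of El-Shatby Maternity Hospital and Madinah Fertility center", so there are two sites.
- **Age** enters eligibility through criterion (i), "advanced maternal age or any other risk factor for POR". That age is recorded for every woman is an inference.

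Each woman is stimulated twice. Group 1 has a follicular and a luteal stimulation in one protocol; for group 2, "This controlled ovarian stimulation will be done twice in two different cycles". The total number of women is 80 under Participants and 90 (45 per group) under Study design.

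**The concern.** With 40 to 45 women per arm, the estimated differences in oocyte and embryo counts will be imprecise. Variation in those counts that age, AMH and centre can predict stays in the error term of an unadjusted comparison. Removing it narrows the confidence interval and raises power without recruiting anyone else.

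The gain is not certain. Each covariate costs a little precision through chance imbalance and lost degrees of freedom, so weak predictors make matters slightly worse. The practical question is how much the covariates must explain before adjustment pays, and what is lost if they explain nothing.

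**Working it through.** **Inputs from the documents.** Total N of 90 or 80 in equal arms; 5% significance level (taken as two-sided, since sidedness is not stated); three covariate degrees of freedom (age, AMH, and one for two centres). The documents give no effect size, SD, power or dropout, so the sample size cannot be reproduced.

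**Assumed.** Unadjusted t-test power of about 80%, which corresponds to a standardised difference of 0.597 at N=90 and 0.634 at N=80; R², the share of within-group variance explained by the covariates, from 0 to 0.30.

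**Step 1: break-even with ordinary standard errors.** For k covariates, the expected variance of the adjusted difference relative to the unadjusted one is

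(1 − R²) × (N − 3) / (N − k − 3).

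With k = 3:

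- N=90: 87/84 = 1.036, so break-even R² = 1 − 84/87 = 3.4%.
- N=80: 77/74 = 1.041, so break-even R² = 1 − 74/77 = 3.9%.

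Allowing for the slightly larger t critical value moves these to 3.5% and 4.0%.

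**Step 2: power** (noncentral t; interval width ratio taken as the square root of the variance ratio).

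| R² | Variance ratio, N=90 | Interval width, N=90 | Power, N=90 | Power, N=80 |
|---|---|---|---|---|
| 0 | 1.036 | +1.8% | 78.6% | 78.4% |
| 0.05 | 0.984 | −0.8% | 80.6% | 80.4% |
| 0.10 | 0.932 | −3.5% | 82.7% | 82.5% |
| 0.20 | 0.829 | −9.0% | 86.8% | 86.6% |
| 0.30 | 0.725 | −14.9% | 90.8% | 90.7% |

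Dividing 90 by the variance ratio gives the equivalent unadjusted sample: about 87, 91, 97, 109 and 124 women.

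**Step 3: do ordinary errors hold up on counts?** In a simulation at N=90 with assumed negative-binomial counts (mean 5), power for Mann-Whitney / t / ANCOVA was 70.2/75.4/73.8% at R²=0, 69.3/75.4/75.8% at 0.05, 70.6/75.8/78.5% at 0.10 and 70.5/76.1/86.6% at 0.30. The loss against the t-test at R²=0 was 1.6 points, and ANCOVA was ahead by R²=0.05. Across the checks run, the simulated type I error of ordinary ANCOVA was 4.1 to 5.4%.

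**Step 4: HC3 standard errors.** These are wider at this sample size. With a normal outcome at 45 per arm, HC3 power was 76.6/78.8/81.9/85.3/89.9% at the five R² values, against about 80% for the t-test, and interval width changed by +4.8/+2.1/−0.6/−6.3/−12.5%. Break-even moves to an R² of about 8 to 10%. That threshold comes from HC3, not from adjustment as such.

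**Step 5: selection.** Eligibility may narrow the spread of age and AMH. If covariate SDs shrink to a fraction u of their unselected values, R² becomes R²u²/(1 − R² + R²u²). For u=0.7, 0.20 becomes 0.098/0.898 = 0.109 and 0.30 becomes 0.147/0.847 = 0.174. For u=0.5, they become 0.050/0.850 = 0.059 and 0.075/0.775 = 0.097. Put through the Step 2 calculation at N=90, these give power of about 83.0, 85.7, 81.0 and 82.5%: a gain of about 1 to 6 points over 80%. Both values of u are assumptions.

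**The case against.** The strongest reply is that nothing is broken. In a properly randomised trial the unadjusted t and Mann-Whitney tests are valid if each woman contributes one total, and no section promises adjustment or stratification. A reader might infer that leaving out covariates, or centre, biases the comparison; the documents do not support that, and it is not claimed.

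The size also rests on assumptions. R² is not in the documents, and neither are the SD or the target difference. Eligibility works against a large R²: criterion (iii) is "an abnormal ovarian reserve test (ORT): AFC less than 5-7 or AMH is less than 1.1 ng/ml", and age enters through criterion (i). The narrowing is only partial, because women qualify as "poor responders defined by Bologna criteria either two or more of the following", or by two earlier poor responses, so not every woman need be older or have low AMH. This objection stands to the extent that the gain cannot be promised.

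A reader might also infer that adjustment is worthwhile only if the covariates explain more than about 10% of the variance. That holds approximately for HC3 errors alone. The arms are equal, and the type I error of ordinary errors stayed close to 5% in simulation, so the extra cost of HC3 buys no shown benefit here.

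Two further points stand. ANCOVA estimates a difference in means, whereas Mann-Whitney compares ranks, so the target changes; in the count simulation, about 5 of the points gained over Mann-Whitney come from that change of test, not from the covariates. And the Statistical analysis section is written in the past tense, so outcome data may already have been analysed.

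**Conclusion.** This is an optional improvement, not an error. With ordinary standard errors, adjustment gains against the t-test once age, AMH and centre together explain more than about 3.5% (N=90) to 4% (N=80) of the variance. From an assumed 80% power, the change runs from a loss of about 1.5 points at R²=0 to gains of about 2.5 points at 0.10, 7 at 0.20 and 11 at 0.30. The break-even depends only on N, equal arms and three covariate degrees of freedom; the power figures rest on the assumed 80% and the assumed R². The conflict between 80 and 90 women needs reconciling but does not alter the conclusion. A definite increase in power should not be inferred, because the R² in these selected women is unknown.

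**What to change.** For M2 oocytes and for embryo number separately, pre-specify one main analysis: ANCOVA of the per-woman total over both stimulations on group, age, AMH (on one scale, for example log, fixed in advance) and centre, with ordinary standard errors, reporting the adjusted mean difference with its 95% confidence interval. State that the target is a difference in means. Keep Mann-Whitney as a sensitivity analysis; HC3 errors may be added as a further check. The pregnancy comparison can stay as chi-square or Fisher.

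The cost is a few lines of analysis text and one model per outcome, plus confirmation that age, AMH and centre are recorded for every woman. The statistical risk is 1.5 to 2 points of power against the t-test if the covariates explain nothing. If outcome data have already been seen, report the adjusted analysis as post hoc and leave the planned tests as the main result.
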